#### FORMAL CARE

7. During the last 3 months, due to your disease, did you have to hire professional services for homecare?	Yes..... ..... No..... .....	1 2
If you have checked "Yes" please complete the subsequent table F. If you have		

		checked "No" please move on to question number 8.	
--	--	---	--

Table F. Please enter the names and description.

Kind of service	Number of days per week	Number of hours per day	Wage per hour
Day homecare			
Night homecare			
Full time homecare			
Housekeeping			

**INFORMAL CARE**

8. During the last 3 months, due to your disease, did you have to accept help from relatives, friends or from professional services for work, which you usually carry out by yourself? For example; for housekeeping or for shopping.

Yes.....  
.....  
No.....  
.....

If you have checked "Yes" please complete the subsequent table G. If you have checked "No" please move on to question number 9.

Table G. Please insert here the average time in hours of help and the average cost of help per week. In case you do not know the cost please insert a question mark.

Kind of help	Average duration per week	Average cost per week
Help from relatives, friends or acquaintances	_____ h	_____ €
Home help	_____ h	_____ €
Professional aids (e.g. Red cross)	_____ h	_____ €
	_____ h	_____ €
	_____ h	_____ €
	_____ h	_____ €

**EMPLOYMENT SITUATION**

9. Are you currently employed?

Yes.....  
.....  
No.....  
.....

	If you have checked "Yes" please move on to question number 10. If you have checked "No" please move on to question number 13.	
10. If you returned to work in the last 3 months, is it the same employment that you had before your illness?	Yes..... ..... No..... .....	1 2
11. During the last 3 months, have you been on sick leave due to your disease (at home or in hospital)?	Yes..... ..... No..... .....  If you have checked "Yes" please complete the subsequent table H. If you have checked "No" please move to question number 12.	1 2

**Table H. Please complete the information.**

Time you were on sick leave	Date from – until (DD-MM-YY)	Date from – until (DD-MM-YY)	Date from – until (DD-MM-YY)
Medically certified absence from work	From _____._____._____ Until _____._____._____	From _____._____._____ Until _____._____._____	From _____._____._____ Until _____._____._____
Reduced hours of work for gradual reintegration	From _____._____._____ Until _____._____._____	From _____._____._____ Until _____._____._____	From _____._____._____ Until _____._____._____

12. During the last 3 months, have you seen a doctor or therapist during your working hours?
	
Yes..... ..... No..... .....
 
If you have checked “Yes” please complete the subsequent table I. If you have checked “No” please move on to question number 14.

---	---

Table I. Please complete the information.

Number of working hours, which	Overall loss of working time
--------------------------------	------------------------------

you spent to see a doctor or therapist		
General practitioner	_____ h	
Nurse	_____ h	
Neurologist	_____ h	
Psychologist	_____ h	
Ambulatory care in hospital	_____ h	
Emergency department	_____ h	
Other (please specify) _____	_____ h	
Other (please specify) _____	_____ h	
13. Which category describes best your status?		Retired..... ..... Retired on medical grounds..... ..... Unemployed..... ..... Student..... .....
		1 2 3 4
14. During last 3 months have you suffered from income loss due to your illness?		Yes..... ..... No..... .....
		1 2
15. Do you have any health-related insurance policy/plan?		Yes..... ..... No..... ..... If you have checked "Yes" please complete question 16. If you have checked "No" you have finished the questionnaire.
		1 2
16. Is your health-related insurance policy/plan public or private?		Public..... ..... Private..... .....
		1 2
17. Please tell us what it covers by ticking one or more of the		Health care costs (i.e. 1

following options:	medical, visits) Medication Income protection Any other (please specify)	2 3 4
	_____	_____

**Frequently asked questions**

*I have had the flu and have therefore visited my doctor, who certified me unfit for work. Do I have to enter the drugs, the doctor visit, the time of sick leave and the time in which I was not able to carry out my housework?*

No, please only enter things, which are directly related to your disease. We do not want to include all treatments and expenses, you had due to other diseases.

*I cannot remember the exact information on the package of my drug. What should I enter?*

Please try to answer as exactly as possible. If you do not have the package of the drug for copying the name from it anymore, please enter the type of drug, e.g. beta blocker.

*I have not received the bill for my alternative practitioner visit yet. What should I do now?*

Please enter a question mark. Unless, from experience, you are quite sure how much the bill will be. In that case, please enter your estimate.

*Due to my ALS disease, I have had expenses, which I do not know where to put, because none of the tables seems to really apply to them. Where should I enter these expenses?*

Please enter all expenses, treatments and applications which you cannot clearly assign to any question, into the questionnaire. Please do not leave out anything that is related to your disease.

## VERSION HISTORY

Version	Date	History list
1.0	19 Apr 2024	Final version

## LIST OF ABBREVIATIONS

8-OHdG	8-hydroxyguanosine
AE	Adverse Event
AESI	Adverse Event of Special Interest
ALS	Amyotrophic Lateral Sclerosis
ALSFRS-R	ALS Functional Rating Score – revised
ALSAQ-40	ALS Assessment Questionnaire-40-Item
BMI	Body Mass Index
CI	Confidence Interval
CRF	Case report form
CSR	Clinical Study Report
DSMB	Data Safety Monitoring Board
EQ-5D-5L	EuroQoL – 5 Dimensions – 5 Levels
GCP	Good Clinical Practice
ICH	International Conference on Harmonisation
ITT	Intent-To-Treat
MedDRA	Medical Dictionary for Regulatory Activities
mITT	Modified Intent-To-Treat
NFL	Neurofilament light
OLE	Open label extension
P75ECD	Neurotrophin receptor p75
PDF	Portable Document Format
PEG	Percutaneous Endoscopic Gastrostomy
PNG	Portable Network Graphics
PT	Preferred Term
Q1	Lower quartile
Q3	Upper quartile
QoL	Quality of life
RMST	Restricted Mean Survival Time
RTF	Rich Text Format
SAE	Serious Adverse Event

SAF	Safety analysis population
SAP	Statistical Analysis Plan
SAS	Statistical Analysis Software
SD	Standard Deviation
SOC	System Organ Class
SVC	Slow Vital Capacity
TEAE	Treatment Emergent Adverse Event
VAS	Visual Analogue Scale
WHO	World Health Organisation

## 1 GENERAL

This Statistical Analysis Plan (SAP) describes in detail the methods and presentation of the data analyses which will be conducted for study FAB 122-CT-2201 by Certara.

This plan is written in agreement with protocol versions (see table), and case report form (CRF) version 3.0, dated 28 Nov 2023.

Version*	Date
V2.0 ITA & NL	24/01/2023
V1.1 FRA	03/04/2023
V2.1 RUS	11/05/2023
V1.1 ESP	01/06/2023
V1.1 POL	01/06/2023
V1.1 POR	07/06/2023
V1.1 GBR	06/07/2023
V1.1 BEL	06/07/2023
V1.3 IRL	06/07/2023
V1.1 GER	10/07/2023
V1.1 SWE	10/07/2023

\*see Protocol versions tracker for more details

The protocol and the (annotated) CRF are the primary source for this document, together with the relevant Good Clinical Practice (GCP) and International Council on Harmonization (ICH) guidelines. Furthermore, sponsor requirements for reporting will be considered.

Additional changes or updates of those documents or requirements may result in a new version of the reporting/statistical analysis plan. This study-SAP is to be finalized prior to database lock for study FAB 122-CT-2201.

The statistical analysis and summary tabulations described in this SAP will provide the basis of the results sections of the clinical study report (CSR) for this trial.

## 2 STUDY INFORMATION

### 2.1 Study Objective(s)

The primary objective of this study is to evaluate the long-term safety of FAB122 in patients with Amyotrophic Lateral Sclerosis (ALS).

The secondary objectives of this study are as follows:

- To evaluate the effect of treatment with FAB122 on overall survival

- To evaluate the effect of treatment with FAB122 on disease progression in patients with ALS
- To evaluate the effect of treatment with FAB122 on cognitive functioning
- To evaluate the effect of treatment with FAB122 on quality of life (QoL).

Due to study early termination, some analysis planned in the protocol will not be performed (see Section 6). This SAP focuses on a subset of analyses related to objectives of safety, overall survival, and disease progression.

## 2.2 Design of the Study

This is a multicenter open-label Phase III extension study to investigate the long-term safety of 100 mg FAB122 once daily as oral formulation in ALS patients.

All patients participating in the main study (ADORE) study will be invited to roll over to FAB122 and to participate in ADOREXT. Patients that discontinued treatment in the main ADORE study for other than safety reasons, will be also invited to re-start treatment with FAB122 in the open label extension (OLE) study. The duration of this OLE was planned to be until the product is commercially available at each participant country, provided good tolerance and safety is proven. The sponsor could also make the decision to terminate the study at any time in case the objectives of the ADORE study are not met.

Patients not willing to continue receiving active treatment in the extension study or that had already discontinued study treatment during the course of the ADORE study for safety reasons, will be asked to be contacted by phone and followed up for vital status.

Subjects rolling over the active treatment will visit the clinic at Baseline (whenever possible, visit 6 or 8 of the main study + 6 weeks in case the OLE is not fully set up) and every 3 months thereafter.

## 2.3 Study medication

Patients will receive 100 mg FAB122 granules for oral solution in single sachets, which has to be dissolved in 100 mL water prior to administration.

## 2.4 Sample size

No formal size calculation has been done for the extension study. The main study plans to include approximately 300 patients. It is anticipated that 200-225 patients might be included in this extension study.

All subjects who completed the full study period in the main ADORE study and providing informed consent to comply with extension trial procedures are eligible to participate in this extension study.

## 2.5 Study assessments

The schedule of assessments is available in Table 1 of the study protocol.

## 3 SUBJECTS FOR ANALYSIS

### 3.1 Analysis populations

#### 3.1.1 Modified Intent-to-treat (mITT and mITTe) Analysis Sets

The mITT analysis set includes all patients who were randomized in the ADORE study and received at least 1 dose of investigational product regardless of any protocol deviation (see Section 6). The mITT population will be used for the analysis of efficacy variables, and statistical analysis will be done “as randomized” in ADORE study. The mITT is considered the primary analysis population for efficacy.

The mITTe analysis set refers to the subset of patients of mITT who enrolled in ADOREXT.

#### 3.1.2 Safety Analysis Set Extension (SAFe)

The SAFe population includes all patients enrolled in ADOREXT who have received at least one dose of the investigational drug during the extension study, irrespective of satisfying other criteria. This population will be used for the analysis of safety and tolerability, and statistical analysis will be done “as treated”. Although all patients will be treated with FAB122 in ADOREXT, data will be presented also using the randomization groups of ADORE study.

### 3.2 Protocol deviations

Following Sponsor review of the protocol deviations, none was found as impacting safety and no formal analysis of protocol deviations was found as required following early termination of the study.

### 3.3 Data Review Meeting

Not applicable / not in the scope of this SAP following early termination of the study.

## 4 STUDY ENDPOINTS

The primary, secondary and safety endpoints of this study are reported in the sections below. Due to study early termination, some analysis planned in the protocol will not be performed (see Section 6). Focus of this SAP are the primary endpoint, the overall survival and survival time. The ALSFRS-R score will also be described.

### 4.1 Primary endpoint

The primary endpoint is the nature, frequency and severity of Treatment Emergent Adverse Events (TEAEs).

### 4.2 Secondary endpoint(s)

- ALSFRS-R and mortality-adjusted change from baseline in ALSFRS-R total score until the end of the study
- Overall Survival, defined as time from study treatment start in ADORE study to death from any cause
- Survival time, defined as time from study treatment start in ADORE study to the occurrence of respiratory insufficiency (insufficiency defined as tracheostomy or the use

of non-invasive ventilation for  $\geq 20$  h per day for  $\geq 10$  consecutive days) or death from any cause

- Change from baseline in SVC until the end of the study
- Mean change in norm standardized ECAS total score
- Change from baseline in the total score on the ALS Assessment Questionnaire-40-Item (ALSAQ-40) until the end of the study
- Change from baseline in EuroQoL – 5 Dimensions – 5 Levels (EQ-5D-5L) until the end of the study
- Change from baseline in Health related QoL Visual Analogue Scale (VAS) score until the end of the study
- Change from baseline in the prognostic ALS biomarker neurofilament light (NFL)
- Change from baseline in the ALS biomarkers creatinine and creatinine kinase
- Change from baseline in the ALS biomarker Urinary extracellular domain of neurotrophin receptor p75 (Urinary P75ECD)
- Change from baseline of oxidative stress biomarker 8-hydroxyguanosine (8-OHdG)
- Cost-Utility analysis of treatment with FAB122

#### 4.3 Safety endpoint(s)

- Parameters derived from vital signs and 12-lead electrocardiogram (ECG)
- Parameters derived from laboratory tests (hematology, biochemistry, urinalysis)
- Proportion of subjects that drop out due to adverse events.

### 5 STATISTICAL ANALYSIS

#### 5.1 General considerations

Appropriate rounding will be performed for the summary statistics: arithmetic mean, median, SD (standard deviation) and confidence limits will be presented with one more decimal than the original data; minimum and maximum values will be presented with the same precision as the original data. In frequency tables, percentages will be presented with 1 decimal. P-values will be presented with 3 decimals, and those smaller than 0.001 will be replaced by <0.001.

Descriptive statistics presented in general summary tables will be the number of non-missing observations (n), mean, SD, minimum, median and maximum for quantitative data. For categorical data, frequency counts and percentages will be determined. The denominator when calculating percentages will be the number of patients in the applicable analysis population. Descriptive statistics will be displayed for all visits that a measurement is collected on, even if the endpoint is only referring to limited visits for the analysis.

Baseline is defined as the last value measured prior to first study treatment administration in ADOREXT study, unless otherwise specified. Typically, baseline data are collected at Visit 6 or 8 of the ADORE study. In case this value is missing for a specific patient in ADOREXT CRF data, but an earlier measurement is collected in ADORE study data, this value will be used as baseline instead. Unscheduled measurements are excluded as baseline value.

## 5.2 Missing or excluded data

For presentation of descriptive statistics of efficacy data, no imputation or sensitivity analysis will be included, and data will be presented ‘as is’. All these analyses will be done on data available at the visit considered. In summary tables, the number of patients without missing data will be presented (per visit, if applicable) unless otherwise specified. In calculations of percentages, the denominator will be the number of patients in the applicable analysis population.

Data of patients from site 5806 will not be included in the ADOREXT analysis, following GCP findings, in accordance with the analysis performed in ADORE study.

Using the most conservative approach, missing/incomplete information related to AEs will be handled as listed below, to indicate an AE as being treatment emergent or presented having a certain intensity/causality. Note that imputed dates/times or intensity/causality will not appear in data listings, but only in descriptive statistics tables (where applicable).

- In case of (partially) missing onset dates, the AE will be handled as follows:
  - If full start date is available, and on or after first dosing date, the AE is considered treatment emergent.
  - In case full stop date is available and prior to first dosing date, the AE is considered prior.
  - If the day part of the start date is missing:
    - The AE is considered treatment emergent if the month and year of the start date are the same or after the month and the year of the first dosing date.
  - If the day and month part of the start date are missing:
    - The AE is considered treatment emergent if the year of the start date is the same or after the year of the first dosing date.
  - In case the start date is completely missing:
    - If stop date is fully available and on/after the first dosing date, the AE is considered treatment emergent.
    - If the stop date is partially missing, but the month and year (or year alone in case of missing month) are after the month and year (or year alone) of the first dosing date, the AE is considered treatment emergent.
  - In case full start date and full stop date are missing, the AE is considered treatment emergent.
- In case intensity is missing for a certain TEAE, it will be regarded as severe.
- In case causality is missing for a certain TEAE, it will be regarded as related.
- In case seriousness is missing for a certain AE, then this is discussed and addressed prior to database lock and unblinding in agreement with the sponsor and the Data Management vendor.

ALS history and randomization data will be inherited from ADORE analysis datasets.

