### 11.3. Description of Statistical Methods

#### 11.3.1. Analysis Populations

Safety Analysis Set: The safety analysis set will consist of all subjects who receive at least 1 dose of IMP in the extension study.

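### SAP 5.2 drops all site 5806 data, safety included, which contradicts the SAFe definition and leaves any events in that site's dosed patients out of the planned safety tables

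*SAP*

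**What the plan says.** SAP 5.2 (Missing or excluded data) sets the rule: "Data of patients from site 5806 will not be included in the ADOREXT analysis". The reason given is "following GCP findings, in accordance with the analysis performed in ADORE study". The rule has no restriction to efficacy, and the conventions for handling incomplete adverse event data follow directly after it.

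The population definitions carry no site exception:

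- SAP 3.1.2 defines SAFe as all patients enrolled in ADOREXT "who have received at least one dose of the investigational drug during the extension study, irrespective of satisfying other criteria". SAP 5.6 bases every safety presentation on SAFe.
- Protocol 11.3.1 says: "The safety analysis set will consist of all subjects who receive at least 1 dose of IMP in the extension study".
- SAP 3.1.1 defines mITT as all patients randomized in ADORE who "received at least 1 dose of investigational product regardless of any protocol deviation". SAP 5.5 bases efficacy on mITT unless otherwise specified.

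The mITT definition points to SAP Section 6, which lists the changes from protocol. Section 6 explains why the mITT set was added but does not mention site 5806. The primary endpoint (SAP 4.1) is the nature, frequency and severity of TEAEs.

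**The concern.** A patient at site 5806 who took one extension dose is inside SAFe under SAP 3.1.2 and outside the analysis under SAP 5.2. A programmer cannot follow both, and a reader of the report cannot tell from the SAFe definition that a site is missing.

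At stake is the completeness of the primary output. If the site dosed patients in the extension, their TEAEs, SAEs, discontinuations due to adverse events and deaths would not appear in the AE overview or the SOC/PT tables, and the denominators would be smaller than the defined population.

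Survival raises a second question. SAP 5.5.2.1 combines ADORE and ADOREXT data, but SAP 5.2 refers only to the ADOREXT analysis. It does not say whether the site's ADORE survival data are dropped too, although the reference to ADORE suggests so. No planned output shows whether the exclusion matters.

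**Working it through.** There is no sample size, power or alpha in the plan to reproduce. The main check is a comparison of texts. The arithmetic only illustrates scale.

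**Comparison of texts**

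1. Scope of the exclusion (SAP 5.2): all data of patients from the site, without separating efficacy from safety.
2. SAFe (SAP 3.1.2): one condition beyond enrolment, a dose in the extension, with other criteria expressly set aside. This conflicts directly with step 1.
3. Protocol 11.3.1: the same single condition. The exclusion therefore also departs from the protocol.
4. mITT (SAP 3.1.1): admits patients whatever their deviations. A site-level GCP exclusion need not be a patient-level deviation, so this is a drafting gap more than a flat contradiction.
5. Record of the change: SAP Section 6 is silent on the site. The disposition summary (SAP 5.4.3) has no category for patients removed by site.
6. Other outputs: no analysis including the site is planned. SAP 9.4 puts listings out of scope. SAP 9.3 does number a deaths item (14.3.2.1) and a TEAE item (14.3.2.2), but these are also ADOREXT outputs and so fall under SAP 5.2.

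**Scale, under an assumed site size**

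Inputs: about 38 sites (Protocol synopsis); 200-225 extension patients and about 300 main-study patients (Protocol 11.2). The documents do not give the number of patients at site 5806. The assumption is a site of average size.

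- Extension patients per site: 200/38 = 5.26 and 225/38 = 5.92, so 5 to 6 patients, or 1/38 = 2.6% of the total.
- ADORE patients per site, if ADORE used the same number of sites: 300/38 = 7.9.

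*Precision.* The 95% upper bound for an event type never observed is 1 − 0.05^(1/n).

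- Planned N = 200: 1.49% with all patients; 1.52-1.53% with 5 or 6 dropped; 1.65% with 20 dropped.
- Planned N = 225: 1.32%; 1.35-1.36%; 1.45%.

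*Chance that the site holds at least one patient with the event.* This is 1 − (1 − p)^n with n = 5.26 to 5.92, taking patients as independent and the rate at the site as equal to the overall rate p.

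- p = 1%: 5-6%
- p = 5%: 24-26%
- p = 10%: 43-46%

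With whole numbers of patients (n = 5 and 6) the ranges are 5-6%, 23-26% and 41-47%. For a larger site of 20 patients the chance is 18% at p = 1% and 88% at p = 10%.

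**The case against.** The strongest reply is that the exclusion is open and reasoned. It stands in a section on excluded data, gives its ground, and follows what was done in ADORE. It can be read as a specific exclusion applied to generally defined sets. If source data at the site could not be verified, putting its events and denominators into SAFe could harm the primary output. The survival comparison is secondary and described as descriptive. Much of this stands: the documents do not show that excluding the site from the main analyses is wrong, and a separate display is easier to defend than inclusion in SAFe. It does not remove the conflict with SAP 3.1.2, the silence of Section 6, or the absence of any output for the site's safety data.

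A reader might also infer more than the documents support:

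- *That known deaths and adverse events are being deleted.* Nothing shows that site 5806 dosed anyone in ADOREXT or had any event. Because mITT draws on all dosed ADORE patients, the rule could be needed even if the site enrolled nobody in the extension.
- *That SAP 3.2 shows the site's safety data to be sound, because it says of protocol deviations that* "none was found as impacting safety". That sentence reports a sponsor review of protocol deviations. The exclusion rests on GCP findings, which the documents do not describe, and the two cannot be equated.
- *That these patients would appear nowhere.* AEs are still recorded and SAEs still reported (Protocol 9.5, 9.6), SUSARs are expedited (Protocol 9.7), and SAP 5.6.1 leaves SUSAR reporting to the pharmacovigilance vendor. The gap is in the SAP's planned outputs.
- *That rare serious events would probably be lost.* At a true rate of 1% the chance that an average site holds a case is only 5-6%. The larger figures belong to events at 5% or 10%, which are not rare.

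**Conclusion.** The point holds as a conflict between SAP 5.2 and the SAFe definition (and Protocol 11.3.1), a weaker mismatch with mITT, and an unrecorded change from protocol. GCP findings and consistency with ADORE may support the exclusion from the main analyses. They do not reconcile the definitions, and they give no reason to leave any safety data from dosed patients at the site without display in a study whose primary endpoint is safety.

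The actual size is unknown, because the documents give neither the number of patients and events at the site nor the nature of the findings. Under the average-site assumption precision hardly changes. What matters is that individual deaths or serious events, if there were any, would not be visible in the report's tables. If the site dosed no one in the extension, one sentence saying so would settle the safety part; the survival part and the definitions would still need correcting.

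**What to change.** 1. Keep the ADORE-consistent main analysis.
2. Show the TEAEs, SAEs, discontinuations due to AE and deaths of any dosed site 5806 patients in a separate table beside the SAFe tables, with a caveat on reliability.
3. Repeat the AE overview and the two survival analyses (overall survival and survival time) with the site included, as a sensitivity analysis. The present SAP 5.2 wording against sensitivity analyses concerns descriptive efficacy data and need not prevent this.
4. Amend SAP 3.1.1 and 3.1.2 to match SAP 5.2, and state whether the site's ADORE survival data are also dropped from the combined analysis.
5. Record the exclusion and its reason in SAP Section 6.
6. Report the number of patients excluded in the disposition table.

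The cost is SAP wording, one extra AE/death table and re-runs of existing programs. Under the protocol the safety data are already collected. The downside is that data of uncertain reliability are displayed, which the separate table and its caveat address.

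### SAP 5.2: with no start date and a partial stop date, a stop in the dosing month (or year) meets no explicit treatment-emergent condition, against the stated conservative approach

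*SAP*

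**What the plan says.** SAP 5.2 (Missing or excluded data) opens its AE rules with a principle: "Using the most conservative approach, missing/incomplete information related to AEs will be handled as listed below". The rules that follow are:

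- Start day missing: the AE qualifies "if the month and year of the start date are the same or after the month and the year of the first dosing date".
- Start day and month missing: the AE qualifies "if the year of the start date is the same or after the year of the first dosing date".
- Start completely missing, stop complete: "If stop date is fully available and on/after the first dosing date, the AE is considered treatment emergent".
- Start completely missing, stop partial (no day, or neither day nor month): the AE qualifies only where the known parts of its stop date "are after the month and year (or year alone) of the first dosing date".
- Last bullet on dates: an AE lacking both the full start date and the full stop date is treatment emergent.

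Only one rule makes an AE prior, and it needs a complete stop date before first dosing. SAP 5.6.1 defines a TEAE as appearing at or after the first extension dose and refers to 5.2 for incomplete dates. SAP 4.1 makes the nature, frequency and severity of TEAEs the primary endpoint.

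**The concern.** The partial-stop rule is the only treatment-emergence rule in the list that excludes the boundary period, and the SAP gives no reason for the difference. An AE known to have stopped in the month of first dosing may have begun on drug, so a conservative rule would flag it. The same holds for a stop known only to be in the dosing year. The sub-bullet does not flag either.

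On the natural reading of the last bullet (no date information at all), the ordering is also odd: an AE with no dates counts as treatment emergent, while one with a stop date compatible with onset on drug does not.

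An AE that fell out here would be missing from the tables of TEAEs, serious TEAEs and TEAEs leading to treatment discontinuation (SAP 9.3). It would also lose the defaults for missing intensity (severe) and missing causality (related), which SAP 5.2 applies only to TEAEs.

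**Working it through.** The documents give no figure on this point, so there is none to reproduce. The check has two parts.

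**1. The rules applied to one case.** Assume first dose on 10 June 2023 and a completely missing start date. The last bullet is read as needing both dates wholly absent.

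| Stop date recorded | As written | With 'same as or after' |
|---|---|---|
| 10 Jun 2023 (complete) | treatment emergent | unchanged |
| May 2023 | not flagged | not flagged |
| Jun 2023 | not flagged | treatment emergent |
| Jul 2023 | treatment emergent | treatment emergent |
| 2023 | not flagged | treatment emergent |
| 2024 | treatment emergent | treatment emergent |
| none | treatment emergent | unchanged |

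The two versions differ only at the boundary: the dosing month, or the dosing year for a year-only stop.

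**2. How wide the boundary is.** Assumptions, not trial data: first doses spread evenly over the 365 days of 2023, and true stop dates spread evenly from 0 to 365 days after first dose. The benchmark is the SAP's own rule for a complete stop date, which would flag all of these. There are 365 × 366 = 133,590 pairs of dose and stop dates.

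- *Month and year known.* In a month of L days, pairs with the stop in the dosing month on or after the dose number L(L+1)/2. Over the year: 7 × 496 + 4 × 465 + 406 = 5,738. Share not flagged as written: 5,738 / 133,590 = 4.3%.
- *Year only known.* Pairs with the stop in the dosing year number 365 × 366 / 2 = 66,795. Share not flagged as written: 66,795 / 133,590 = 50%.
- *With 'same as or after'.* Both shares are 0%.

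Seen from within the boundary period, about half of the possible stop days fall on or after first dose:

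- dosing month: 5,738 / (7 × 961 + 4 × 900 + 784) = 5,738 / 11,111 = 52%;
- dosing year: 66,795 / 365² = 66,795 / 133,225 = 50%.

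**The price of the change.** The inclusive rule also flags some AEs that in truth ended before dosing. For stops spread evenly over the 180 days before first dose (365 × 180 = 65,700 pairs):

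- month-and-year stops: 5,373 / 65,700 = 8.2%, where 5,373 = 7 × 465 + 4 × 435 + 378;
- year-only stops: 49,410 / 65,700 = 75.2%, where 49,410 = 16,290 + 184 × 180.

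That is the direction of error a conservative rule accepts, and the SAP already accepts it for partial start dates.

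**The case against.** **No rule excludes these AEs.** A reader might infer that the SAP drops them or classes them as not treatment emergent. It does neither. They fail one sufficient condition and are left unassigned, and the only rule for prior AEs does not reach them. A program built on one-directional rules would probably default them to not treatment emergent, but that is a likely default and not a rule in the text. This stands.

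**The last bullet may catch them.** Elsewhere in the list 'full' describes a complete date, while total absence is called completely missing. On that usage, an AE with no start date and a partial stop date lacks both full dates and is treatment emergent, and the odd ordering disappears. Against this, the reading makes the partial-stop sub-bullet redundant and overrides the limits on partial start dates, so it is the less natural one. It cannot be excluded, and the ambiguity itself needs correcting.

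**Size.** A reader might infer from the country protocol dates (January to July 2023) and the SAP date (April 2024) that most patients were first dosed in 2023, so that year-only stops in 2023 would be widely affected. The documents do not support this: version dates are not dosing dates, no first-dose dates are given, and the start date must also be completely missing.

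**Data controls.** Investigators must give the onset date (Protocol 9.5), AEs are actively collected at each visit (Protocol 8.2), and completeness checks with queries are planned (Protocol 12.3). These make such records uncommon but do not mend the rule.

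**Impact.** The SAP plans only descriptive AE tables. The overview also counts any serious AE and any AE leading to death without the treatment-emergent restriction (SAP 5.6.1), so those events stay visible there. The tables by SOC and PT still depend on the rule.

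**Conclusion.** The point holds as a minor inconsistency in a rule that feeds the primary endpoint. The strict 'after' departs from the neighbouring rules and from the principle stated above them. On the natural reading, it leaves AEs that may have begun on drug without a treatment-emergent classification.

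The number of affected records is unknown and probably small, since each needs a completely missing start date together with a partial stop date. The 4% and 50% are shares of that record type under assumed even dates, not shares of all AEs. Whether any AE is actually lost depends on how the last bullet is programmed, which the SAP does not settle.

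**What to change.** Three edits to SAP 5.2:

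1. In the partial-stop sub-bullet, replace 'are after' with 'are the same as or after'.
2. Reword the last date bullet to say that the start date and the stop date are both completely missing.
3. Add a default: an AE is treatment emergent unless its available date parts show that it started or ended before first dosing.

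The first edit alone would leave the ambiguous bullet in place and supply no default, so all three are needed.

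The cost is a few sentences and one comparison operator in the program. Against the natural reading, TEAE counts can only stay equal or rise. If the program already takes the last bullet broadly, the second edit could instead remove AEs whose partial dates place them wholly before first dosing. The current implementation should therefore be checked when the text is changed.
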